1 **PROTOCOL SUMMARY** 1.1 SYNOPSIS Title: CD24Fc Administration to Decrease LDL and Inflammation in HIV Patients, Both as Markers of Efficacy and Cardiovascular Risk Reduction (CALIBER) **Study Description:** This is a phase 2, randomized, double-blinded, placebo-controlled clinical trial. The intervention drug will be CD24Fc (IV infusion). A cohort of 64 subjects with HIV on antiretroviral therapy will be randomized in a 1:1 fashion to be administered 3 doses of CD24Fc (240mg IV infusion) or placebo q2w during a 4-week window, followed by a 24-week follow-up window to assess safety and changes in LDL. **Objectives:** Primary Objectives: 1. To determine the safety and tolerability of CD24Fc during the 4-week dosing period and a 24-week follow-up period in a cohort of HIV patients. 2. To evaluate the change in LDL during a 4-week dosing period of CD24Fc and a 24-week follow-up period. Secondary Objectives: To evaluate the effect of CD24Fc on the following variables between the placebo and intervention arms in comparison with baseline values: 1. Levels of total cholesterol, HDL, and triglycerides 2. Markers of immune activation (CD4 and CD8 T cells, IFN, TNF, sCD14) 3. Size of HIV reservoirs 4. Myocardial damage (measured by Troponin I and T) 5. Hepatic steatosis, as determined by transient elastography 6. Leptin 7. Hemoglobin A1c 8. Presence of anti-drug antibody (ADA) and temporal correlation to any adverse events, and its effect on PK (For first 6 subjects). 9. The pharmacokinetics (PK) and pharmacodynamics (PD) of CD24Fc in the first 6 randomized subjects. **Exploratory Objectives:** 1. To assess the effect of CD24Fc on aortic vascular inflammation as measured by standardized uptake value of arterial FDG by PET/CT. We will select 12 subjects with an LDL>125 to have the imaging study. 2. To assess the effect of CD24Fc on the inflammatory markers hs-CRP and GlycA. 3. To assess the effect of CD24Fc on the CEC and NMR lipoproteins. 4. To assess the effect of CD24Fc on endothelin-1.

Endpoints:	 Primary Endpoints: 1. Incidence and severity of any adverse events (AEs) during the administration of drug and 24 weeks after completion. Safety will be evaluated by assessment of clinical laboratory tests, physical examination at various time points during the study, and by the documentation for AEs.
	 The percentage reduction in LDL level from the baseline (predosing) to 2 weeks after the last treatment.
	Secondary Endpoints:
	 Percent change in levels of total cholesterol, HDL, and triglycerides from baseline to Weeks 6 and 28 between placebo and intervention arms.
	 Percent change in markers of immune activation (CD4 and CD8 T cells, IFN, TNF, sCD14) from baseline to Week 6 and 28 between placebo and intervention arms.
	3. Change in proviral DNA from baseline to Week 6 and Week 28 between placebo and intervention arms.
	 Percent change from baseline to week 28 in Troponin I and T between placebo and intervention arms.
	 Change in percent of hepatic steatosis (by CAP measurement) and fibrosis (by KPA) as determined by transient elastography from baseline to week 28 between placebo and intervention arms.
	 Percent change in leptin from baseline to Week 6 and Week 28 between placebo and intervention arms.
	 Percent change in hemoglobin A1c from baseline to Week 6 and 28 between placebo and intervention arms.
	8. PK and PD assessments (For 6 subjects)
	9. Presence of ADA in all subject with temporal correlation to any adverse events, and its effect on PK (For first 6 subjects).
	10. Changes in IL-6, apoB, Lp(a), urine albumin to creatinine ratio before and after treatment.
	Exploratory Endpoints: 1. Change in vascular inflammation as evidenced by aortic FDG uptake by
	FDG-PET/CT will be assessed before and after therapy. The arterial uptake of FDG is measured by the standardized uptake value (SUV) max divided by the venous SUV mean yielding a target to background ratio (TBR).
	 Changes in hs-CRP and GlycA before and after treatment. Changes in CEC and NMR lipoproteins before and after treatment. Changes in endothelin-1 before and after treatment.
Study Population:	64 adults with HIV infection (age 50 and older) on antiretroviral therapy (ART) with HIV viral suppression for at least 2 years. Subjects will be recruited from the Baltimore, MD and Washington, DC regions.

CALIBER OncoImmune CD24Fc-003 Protocol HP-00086029

Version 5.0 November 12, 2020

Phase: Description of Sites/Facilities Enrolling Participants:	2 University of Maryland Institute of Human Virology Clinical Research Unit (IHV/CRU) [name] National Institutes of Health Clinical Center Radiology (Bldg 10) [name] [name], MD 20814
Description of Study Intervention:	Human CD24 (also known as cluster of differentiation 24 or heat stable antigen (HSA)) is an 80 amino acid glycosyl-phosphatidyl-inositol (GPI)- anchored glycoprotein expressed on the membrane surfaces of hematopoietic and non-hematopoietic cells. Recombinant fusion protein, CD24Fc, is composed of the extracellular domain (ECD) of human CD24 fused to the hinge and Fc region of human IgG. It has been used for the treatment of autoimmune diseases and Graft vs Host Disease. Doses of 240mg have been shown to be safe, well-tolerated, and effective in reducing LDL.
Study Duration:	2 years
Participant Duration:	28 weeks

1.2 SCHEMA

Week	0	2	4	6	16	28
		ervention: CD24 infusion, Q2W x			Follow up	
		ervention: Placel infusion, Q2W x	- 1 - L		Follow up	
	Primary Endpoints: Safety evaluation and LDL					
	Secondary Endpoints: Changes in cholesterol, HDL, triglycerides, markers of immune activation, proviral DNA, Troponin I, Leptin, HbA1c, hepatic steatosis, ADA, PK and PD.					
	Exploratory Endpoints: Change in arterial inflammation (FDG-PET)					

1.3 SCHEDULE OF ACTIVITIES (SOA)

	Screening ⁺ Day -55 to - 14	Day -55 to -1	Day -55 to -1#	Day 0	Wk 2*	Wk 4*	Wk 6^	Wk 16^	Wk 28^
Informed Consent	Х								
Medical History & Physical Exam ¹	Х			Х			Х	Х	Х
Height, Weight, and BMI	Х								Х
Vital Signs	Х			Х	Х	Х	Х	Х	Х
Medication Reconciliation	Х			Х	Х	Х	Х	Х	Х
Adverse Event Review and Evaluation				Х	Х	х	Х	Х	х
CMP, CBC with diff, PT/INR, Urinalysis	Х			Х	Х	Х	Х	Х	Х
CD4 count and HIV VL	Х			Х	Х	Х	Х	Х	Х
Hepatitis B panel (surface antigen, core antibody, surface antibody)	Х								
Hepatitis C Ab with reflex RNA	Х								
Hemoglobin A1c	Х						Х		Х
Lipid panel (Fasting)	Х		Х	Х	Х	Х	Х	Х	Х
Troponin I and T	Х						Х		Х
Leptin (Fasting)	Х		Х				Х		Х
ECG (once at Screening and Wk 6; pre-dose and 2 hrs post-dose during dosing visits)	х			Х	Х	Х	Х		
Serum hCG (women of child-bearing potential)	Х								Х
POC Urine hCG (women of child-bearing potential)				Х	Х	Х	Х	Х	
PK of ART and CD24Fc before (and 2 hrs post-dose for Day 0 to Week 4)- first 6 subjects				Х	Х	Х	х	Х	х
Anti-drug antibody%				Х			Х		Х
Immunology labs (for CD4:CD8, sCD14, proviral DNA), inflammatory cytokines	Х			х	Х	х	х	х	х
GlycA, CEC, NMR lipoproteins ²				Х			Х		Х
hsCRP, IL-6, apoB, Lp(a), UACR	Х			Х	Х	х	х	х	Х
Endothelin-1	Х								Х
CD24Fc Infusion		Ī		Х	Х	Х			
Transient elastography with CAP	Х		х						Х
FDG PET/CT (NIH) ³		Х							Х

* Screening tests within the last 8 weeks prior to screening visit that have been done as part of routine medical care or at an outside

facility can be used. Screening window of 8 weeks with more than 2 weeks between screening and Day 0.

*Study Visits for Weeks 2-4 include a window of +/-4 days

^Study Visit for Weeks 6, 16 and 28 include a window of +/- 1 week except for FDG PET/CT, which will include a window of +/-30 days

¹ Targeted history and exam will be performed as needed for symptoms or lab abnormalities

 $^{\rm 2}$ Only for subjects completing the optional FDG-PET/CT testing

³ See protocol section 8.1.1.2 for criteria leading to FDG PET/CT testing

If subject is not fasting at screening, may return for fasting labs and Transient Elastography prior to Day 0

% also done for suspected immune-related adverse events.

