Importantly, the drug has advantages over conventional immunosuppressants as it does not cause general immune suppression and use of high doses of CD24Fc does not block antibody response in non-human primates. Furthermore, an important function of allogeneic stem cell transplantation is to use donor T cells to eliminate allogeneic leukemia cells. This effect is called GVL. Importantly, treatment of CD24Fc, which prevented GVHD had no effect of GVL in the mouse model. Finally, extensive studies in non-human primate demonstrate that CD24Fc does not suppress antigen-specific immune response, which suggest that CD24Fc will not likely increase risk of infection. Regardless, eligibility criteria in this study excludes subjects that are considered at risk for uncontrolled infections. Serum samples will be evaluated for autoantibodies as indicated in the SOA. In the Phase IIa trial, the rate of fungal, bacterial and viral infections was not significantly increased. Instead, there seemed to be a trend of reduced CMV reactivation.

In this trial, HIV patients with anti-retroviral treatment may have increased risk of infections. However, the eligibility criteria in the planned study exclude subjects that are considered at risk for uncontrolled infections.

Infusion Reactions: Infusion reactions have not been observed in the Phase 1 or Phase IIa clinical trials. However, the administration of any recombinant protein has the potential to elicit infusion reactions. CD24Fc includes the Fc portion of human IgG1. After target binding, CD24Fc may induce FcγR crosslinking, which has been associated with infusion reactions for some therapeutics.

Infusion reactions may include events such as changes in vital signs, fever, difficulty breathing, hypotension, generalized or facial edema, nausea, chills, mental status changes, urticaria or vomiting during or up to 2 hours following infusion. The Phase IIa Clinical Protocol incorporated generalized procedures designed to closely monitor, minimize and manage any potential infusion reactions and initially was administered only on an inpatient hospital unit. However, the protocol was amended to allow CD24Fc dosing to be administrated in outpatient clinics for the multi-dosing cohort of 8 patients.

in this study, patients will be monitored before, during, and for 2 hours post infusion to assess for infusion-related reactions.

Exacerbation of Immune Responses:

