5.2 EXCLUSION CRITERIA

An individual who meets any of the following criteria will be excluded from participation in this study:

- 1. Current or prior history of any of the following:
 - a. Clinically significant illness (other than HIV) or any other major medical disorder that may, in the opinion of the investigator, interfere with the subject treatment, assessment of compliance with the protocol; subjects currently under evaluation for a clinically-significant illness (other than HIV) are also excluded
 - b. Poor venous access interfering with required study blood collection
 - c. Solid organ transplantation
 - d. Significant pulmonary disease, significant cardiac disease, or porphyria
 - e. Uncontrolled chronic hepatitis B infection (surface antigen positive with detectable HBV DNA as noted in patient's medical documentation from a treating physician)
 - f. Chronic hepatitis C infection (current active only)
 - g. Unstable psychiatric disease. (Subjects with psychiatric illness that is well-controlled on a stable treatment regimen or currently not requiring medication may be included.)
 - h. Any malignancy or its treatment that in the opinion of the PI may cause ongoing interference with host immunity; subjects under evaluation for malignancy are not eligible.
- 2. Abnormal hematological and biochemical parameters at screening, unless the test has been repeated and at least one subsequent result is within the acceptable range prior to study drug administration, including:
 - a. Neutrophil count <750 cells/mm³
 - b. Hemoglobin level <10 g/dL
 - c. Platelet count ≤50,000 cells/mm³
 - d. Estimated glomerular filtration rate, calculated by the chronic kidney disease epidemiology collaboration formula: <30 mL/min/1.73 m²
 - e. ALT or AST level ≥5 times upper limit of normal (ULN)
 - f. Total bilirubin level ≥2.0 times ULN, except in subjects with Gilbert's syndrome or other clinical explanation at the discretion of the PI
 - g. Albumin level <3 g/dL
- 3. Poorly controlled diabetes as indicated by a screening glycosylated hemoglobin (HbA1c) >10
- 4. Need for the use of the following medications from 21 days prior to the start of study drugs through the end of treatment:
 - a. Hematologic stimulating agents, erythropoiesis stimulating agents (ESAs), granulocyte colony stimulating factor (GCSF, thrombopoietin (TPO) mimetics

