8.1.1.1 SCREENING

Each subject will provide informed consent of his/her free will prior to commencement of any study procedures according to ICH and Code of Federal Regulations (CFR). Each subject will be provided a copy of the signed informed consent form.

After a participant has provided informed consent, the Investigator and other study personnel will determine if they are eligible for participation in the study. Screening may begin up to 8 weeks prior to dosing with at least 14 days before Day 0.

Screening will include a review of the inclusion/exclusion criteria and completion of all screening procedures. Screening tests within the last 8 weeks prior to screening visit that have been done as part of routine medical care or at an outside facility can be used if within the acceptable time frame. Screening procedures do not need to be repeated within the 8-week screening window unless clinically indicated. Once the screening window has elapsed, subjects may be rescreened at the discretion of the PI.

At the screening visit, participants will have an H&P (including vital signs), height, weight and BMI assessment, and a medication reconciliation. Laboratory tests including CMP, CBC, HIV VL, CD4, PT/INR, hemoglobin A1c, Hepatitis B panel, Hepatitis C antibody and reflex RNA, and Troponin I and T will be collected. ECG will be done to assess for abnormalities. Females of child-bearing potential will have a serum hCG tested. Immunology labs looking at CD4 and CD8 by flow, sCD14, and inflammatory cytokines will also be done. If a subject is fasting, the procedures in section 8.1.1.3 including transient elastography may be done at this visit instead of at the "Fasting Lab Visit".

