- Lipid Panel- serum (fasting). This assay will be done through LabCorp. This test includes Cholesterol, total; high-density lipoprotein (HDL) cholesterol; low-density lipoprotein (LDL) cholesterol (calculation); triglycerides; very low-density lipoprotein (VLDL) cholesterol (calculation).
- Hepatitis B panel- HBV Evaluation Panel, serum or plasma. This assay will be done through LabCorp. This test includes Hepatitis B core antibody, total; hepatitis B surface antibody, qualitative; hepatitis B surface antigen
- Hepatitis C Ab with reflex RNA- Hepatitis C Virus (HCV) Antibody with reflex to quantitative realtime PCR, serum or plasma. This assay will be done through LabCorp.
- Serum hCG- human chorionic gonadotropin, beta-subunit, qualitative, serum. This assay will be done through LabCorp. A serum hCG will be done for females of child-bearing potential, at the screening visit.
- Urine hCG- human chorionic gonadotropin, beta-subunit, qualitative, urine. This will be a pointof care assay. A urine hCG will be done for females of child-bearing potential before drug dosing, using a point-of-care urine hCG assay.
- Troponin I and T- In conjunction of cardiovascular inflammation measurement, we will also assess myocardial damage using a validated, sensitive cardiac troponin I and T assays (through LabCorp) will be used for all subjects run as batched samples.

- Leptin- serum or plasma (fasting). Used as a marker for lipodystrophy.
- hsCRP (high-sensitivity CRP), serum or plasma. This assay will be done through LabCorp.
- IL-6 (Interleukin- 6), serum or plasma.
- Apo B (apoliprotein B), serum. This assay will be done through LabCorp.
- Lp(a) (Lipoprotein a), serum. This assay will be done through LabCorp.
- Urine albumin /creatinine ratio, random urine. This assay will be done through LabCorp.
- Pharmacokinetic analyses- done for the first 6 subjects receiving CD24Fc.
 For PK analysis, blood samples will be collected prior to drug infusion at weeks 0, 2, 4, 6, 16, 28 before and 2 hours post dosing of CD24Fc as applicable. A +-/10-minute window around each draw point will be allowed. At weeks 6 and 28, a blood sample for PK will also be collected in order to demonstrate a decrease in drug concentration after dosing completion on week 4.

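### Exclusion 1e depends on HBV DNA that screening never measures, so a surface-antigen-positive, viraemic participant with no DNA on file, or only an old undetectable result, is not excluded by it

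*Combined protocol and SAP*

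**What the plan says.** Exclusion 1e in section 5.2 covers uncontrolled chronic hepatitis B, which it defines as "surface antigen positive with detectable HBV DNA as noted in patient's medical documentation from a treating physician". The lead-in to exclusion 1 is "Current or prior history of any of the following".

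The hepatitis B testing is described in three places, and they agree:

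- Section 1.3, Schedule of Activities (SoA): "Hepatitis B panel (surface antigen, core antibody, surface antibody", marked at screening only.
- Section 8.1.1.1, screening visit: "hemoglobin A1c, Hepatitis B panel, Hepatitis C antibody and reflex RNA, and Troponin I and T will be collected".
- Section 8.2, assays: "This test includes Hepatitis B core antibody, total; hepatitis B surface antibody, qualitative; hepatitis B surface antigen".

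None of the three lists HBV DNA, or a reflex to it when surface antigen is positive. HBV DNA is named only in exclusion 1e.

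The other two viruses are handled differently. The SoA line for hepatitis C is "Hepatitis C Ab with reflex RNA", and section 8.2 specifies a reflex to quantitative PCR. For HIV, inclusion 9 in section 5.1 asks for two years of documented suppression and also for an RNA result below 50 copies/mL at screening.

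On infection risk in this population, section 2.3.1 states that "the eligibility criteria in the planned study exclude subjects that are considered at risk for uncontrolled infections".

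**The concern.** Exclusion 1e turns on two facts. The trial measures one of them (surface antigen) and borrows the other (DNA) from outside records. The plan does not say how recent the borrowed result must be, or what to do when a participant is surface-antigen positive and no DNA result exists. A positive surface antigen at screening triggers no defined next step.

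Two things are at stake. First, section 2.3.1 offers the eligibility criteria as the safeguard against uncontrolled infection for an agent that acts on immune pathways. For hepatitis B, 1e is the only specific criterion. Second, adverse events and laboratory tests make up the first primary endpoint, and confirmed ALT or AST rises relative to Day 0 are withdrawal criteria in section 7.2. Without a baseline DNA value, it is harder to judge whether one participant's rise reflects hepatitis B or the study agent.

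**Working it through.** The plan gives no figure to reproduce, and no formula decides the point. The check is whether exclusion 1e can be determined from what the plan collects.

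**1. What is collected at screening**

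| Virus | Serology or history | Current viraemia measured in the study? |
|---|---|---|
| Hepatitis B | Surface antigen, core antibody, surface antibody | No |
| Hepatitis C | Antibody | Yes, by reflex RNA |
| HIV | Two years of documented suppression | Yes, RNA at screening |

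**2. Does the 8-week limit on outside results apply?** Section 8.1.1.1 and the SoA footnote accept outside results from the 8 weeks before the screening visit, but only for screening tests. HBV DNA is not a listed screening test, so this limit does not govern the chart DNA result that 1e uses.

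**3. Outcome under 1e for a person who is surface-antigen positive and viraemic at screening**

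| HBV DNA in the treating physician's records | Excluded by 1e? |
|---|---|
| Recent, detectable | Yes |
| Old, detectable | Yes, because the lead-in covers prior history |
| Old, undetectable | No |
| None on file | No |

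The gap is the last two rows.

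**4. Do other criteria close it?**

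- Exclusion 1a has a discretionary part (illness that the investigator thinks may interfere) and a categorical part (subjects under evaluation for a clinically significant illness). The second applies only if someone starts a work-up, which the plan does not require.
- Exclusion 2e removes ALT or AST at or above 5 times the upper limit of normal. A viraemic person below that limit passes.
- Exclusion 8 is investigator judgement.

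None of these requires an HBV DNA result.

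**5. Upper bound on the number affected.** The documents give no surface-antigen prevalence. Take 2% to 8% as an assumption for illustration only.

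- Of the 110 to be screened (section 5.5): 110 × 0.02 = 2.2 and 110 × 0.08 = 8.8, so about 2 to 9.
- Of the 64 enrolled: 64 × 0.02 = 1.3 and 64 × 0.08 = 5.1, so about 1 to 5.

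These count everyone who is surface-antigen positive. The gap population is that count multiplied by three further fractions: currently viraemic; no DNA on file or only an old undetectable result; and missed by 1a, 2e and 8. The documents give none of the three. Each is at most 1, so the counts are ceilings and the true number may be zero. The enrolled figure is looser still, because it ignores the people whom 1e removes on charted detectable DNA.

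**6. Weight of one case.** With 64 randomised 1:1, each arm has 32, and 1/32 = 3.1%. If one hepatitis B flare occurred, it would be 3.1% of an arm in descriptive safety tables, for which section 9.4.3 plans no inferential analysis.

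**The case against.** The strongest reply is that reliance on the chart is deliberate. Exclusion 1e names its own evidence source, and inclusion 12 requires every participant to have a primary care doctor, so a record should exist. That stands: this is a design choice, and no two sections contradict each other. It does not answer what happens when the record holds no DNA result or an outdated one.

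A reader might infer that any viraemic participant with an old DNA result gets in. The lead-in to exclusion 1 rules this out, because an old detectable result still excludes. Nor does escaping 1e make a person eligible outright, since 1a, 2e or 8 may still apply.

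A reader might also infer that liver signals could not be told apart from hepatitis B. That is too strong. The trial is randomised and placebo-controlled, surface-antigen status is known at screening, and the SoA lists a metabolic panel at screening and at every visit from Day 0 (the Week 4 text in 8.1.1.6 omits it). The withdrawal limits for transaminase rises are relative to Day 0. Section 8.3 has abnormal results repeated until they normalise and/or are adequately explained, and nothing prevents HBV DNA testing at that point. What remains is harder attribution in the individual case.

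Finally, section 2.3.1 argues that the agent is not broadly immunosuppressive, and some may expect antiretroviral therapy to control hepatitis B anyway. But the same section still relies on eligibility to handle infection risk, and the protocol nowhere says that antiretroviral therapy settles hepatitis B status. Exclusion 1e is not conditioned on regimen.

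**Conclusion.** The point holds in a limited form. Followed exactly, exclusion 1e fails to exclude a surface-antigen-positive, currently viraemic person with no DNA on file or only an old undetectable result, and the scheduled tests would not reveal it. That goes beyond missing detail, because the rule as stated can pass people whom it is meant to keep out. The other criteria reduce the gap without closing it.

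The size is unknown and probably small. It would be wrong to read the illustrative counts as the number of participants harmed: they rest on an assumed prevalence and are upper bounds. The sample size and the LDL analysis are not in question. The change is worth making because it is cheap and serves a safety purpose that the protocol itself states.

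**What to change.** In the SoA, section 8.1.1.1 and section 8.2, add reflex HBV DNA on the screening sample when surface antigen is positive, in the same form as the hepatitis C line. Then reconcile exclusion 1e with those three places, so that the screening result is used in addition to the treating physician's record.

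It should not replace the record. A surface-antigen-positive person with charted detectable DNA is now excluded through prior history. If only the screening value counted, that person would pass with an undetectable result, and the exclusion would become narrower.

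The cost is a short amendment and one PCR per surface-antigen-positive person screened (about 2 to 9 tests under the assumed prevalence), with no extra visit. The downside is those added tests and possibly one or two more screen failures.
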